4.8 Study size

Uterine perforation is an uncommon event; 1.3 cases per 1,000 IUD insertions were reported in the EURAS-IUD at 1-year follow-up (Heinemann et al., 2015). The EURAS-IUD also showed that the incidence was higher in breastfeeding women and with early (≤ 36 weeks) postpartum insertion.

Based on results from the validation/feasibility study, the expected number of women with insertion of an IUD available through 30 June 2018, from the four health care systems is approximately $N = 225,000$, with breastfeeding status available for approximately 60,000 of the total. For the two primary objectives related to the risk of uterine perforation, the power of the study is based on detecting a difference in the estimated risk of uterine perforation with respect to (1) breastfeeding status at the time of IUD insertion and (2) time of IUD insertion after pregnancy delivery. The null hypothesis is no difference in risk of perforation by breastfeeding or time of IUD insertion. There will be no adjustment for multiplicity.

For a two-sided test of the hazard ratio (Schoenfeld, 1983), based on a perforation risk of 1.3 per 1,000 insertions in the 1 year after insertion, a hazard ratio of 2.0 can be detected at the two-sided $\alpha = 0.05$ significance level with the following power:

- 85% for breastfeeding versus not breastfeeding (assuming 60% of women with available breastfeeding status are breastfeeding)
- 73% for ≤ 6 weeks, > 99% for > 6 and ≤ 14 weeks, and 73% for > 14 and ≤ 52 weeks versus > 52 weeks postpartum IUD insertion (assuming a postpartum period allocation of 5:20:5:70)

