There were approximately 325,000 IUD insertions identified during the time frame of the validation/feasibility study (i.e., end date, 30 September 2015), and approximately 65% of those occurred after at least 12 months within the data source. In approximately 90% of IUD insertions, this was the first observed insertion for each woman. Approximately 30% of women were identified as having an IUD inserted within the first 52 weeks postpartum. Based on these results and assumptions—approximately three additional years of data more than the validation study and allowing for a loss of approximately 15% of the insertions due to missing data and the propensity score trimming process (Section 9.7.1.3.2)—the number of first insertions of an IUD available through June 2018 from the four health care systems is anticipated to be approximately 225,000, with breastfeeding status available for approximately 60,000. For the two primary objectives related to the risk of uterine perforation, the power of the study is calculated for differences in the estimated risk of uterine perforation with respect to (1) breastfeeding status at the time of IUD insertion and (2) time interval of the IUD insertion following delivery. The null hypothesis to be tested for primary objective 1 is that the natural logarithm of the adjusted summary perforation hazard ratio for breastfeeding versus not breastfeeding at the time of IUD insertion is equal to 0. Using information from validation study, the expected allocation ratio of breastfeeding versus not breastfeeding is 60:40 for this objective. Three null hypotheses to be tested for primary objective 2 are that the natural logarithm of the adjusted summary perforation hazard ratio for early (i.e., ≤ 6 weeks postpartum, > 6 and ≤ 14 weeks, > 14 and < 52 weeks) versus later (i.e., > 52 weeks) postpartum IUD insertion is equal to 0. Based on information from the validation study, the expected allocation ratio of the corresponding postpartum period categories is 5:20:5:70 for this objective.

Power calculations for the expected number of IUD insertions were performed using PASS 14 software (NCSS, LLC, Kaysville, Utah) for a two-sided test of the hazard ratio (Schoenfeld, 1983). Table 4 indicates the power to detect various hazard ratios at the two-sided $\alpha = 0.05$ significance

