level based on a perforation risk of 1.3 per 1,000 insertions and the percentage of insertions expected for the exposure groups of interest, i.e., breastfeeding versus not breastfeeding and early versus late postpartum insertion for the two cutpoints of interest.

Table 4. Power to detect hazard ratio for uterine perforation based on anticipated number of intrauterine device insertions and exposure group allocation

Exposure groups	Number of insertions expected	Allocation % (exposed: unexposed)	Hazard ratio that can be detected (% power)				
			1.5	1.75	2.0	2.25	2.5
Primary objective, 1: Breastfeeding vs. not breastfeeding	60,000	60:40	42	68	85	94	98
Primary objective, 2: Categories of postpartum insertion timing: ≤ 6 weeks vs. > 52 weeks, including women without a recorded delivery within the past 52 weeks	168,750	5:70	32	54	73	85	92
Primary objective, 2: Categories of postpartum insertion timing: > 6 and ≤ 14 weeks vs. > 52 weeks, including women without a recorded delivery within the past 52 weeks	202,500	20:70	78	97	> 99	> 99	> 99
Primary objective, 2: Categories of postpartum insertion timing: > 14 weeks and ≤ 52 weeks vs. > 52 weeks, including women without a recorded delivery within the past 52 weeks	168,750	5:70	32	54	73	85	92

Table 5 displays the power to detect various hazard ratios at the two-sided $\alpha = 0.05$ significance level for the risk of perforation among LNG-releasing versus copper IUDs based on a perforation risk of 1.3 per 1,000 insertions and the percentage of insertions expected for the exposure groups of interest, i.e., timing of postpartum insertion and breastfeeding versus not breastfeeding.*

* These numbers are provided per the FDA request in the letter of 18 May 2016 to address the request to account for “sufficient number of users of both types of IUDs to allow secondary analyses of the comparative safety of LNG IUSs vs. copper IUDs with regard to early postpartum insertion and breastfeeding status at the time of insertion.” These power calculations are not necessarily directly linked to objectives, but rather indicate that adequate data are likely to be available to characterize comparative safety of LNG IUSs and copper IUDs.

Table 5. Power to detect hazard ratio for uterine perforation for LNG versus copper IUDs based on anticipated number of intrauterine device insertions and an 80% (LNG) versus 20% (copper) exposure group allocation

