Propensity scores will be used to measure the probability of being "exposed" given specified covariates. The propensity scores will be developed with respect to the outcomes being assessed

within this study and thus is not outcome blinded. This is a variable selection technique that elicits good results for propensity score models (Brookhart et al., 2006).

The results of this study are dependent on accurate capture of data and definitions of variables. Since variables will be determined from diagnosis codes (ICD-9-CM, ICD-10-CM*), Current Procedural Terminology codes, medication codes (National Drug Codes), and clinical notes (i.e., via NLP) there is a possibility of misclassification. Algorithms for the outcome variables, uterine perforation and IUD expulsion, have been validated in these four databases prior to use of ICD-10-CM coding. No formal validation of the algorithms with ICD-10-CM codes to identify uterine perforation or IUD expulsion will be done. However, the rates of these outcomes will be reviewed prior to and after the implementation of ICD-10-CM coding to ensure consistency over time. For variables that have not been validated in these databases, algorithms validated in other data sources (e.g., administrative claims) will be used to identify conditions and medication dispensing, when available. In addition, the study team will develop and share conceptual definitions across data sources to standardize approaches to data capture.

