There is potential for underreporting of outcomes within the data sources since women will need to seek treatment in order to have an outcome diagnosed. Asymptomatic perforation or IUD expulsion may not be captured. In addition, there may be a lag time between occurrence of perforation or IUD expulsion and the time that the woman seeks treatment. So there is the possibility of missing outcome occurrence. However, this approach is representative of the way that these outcomes would appear within clinical practice, is similar to EURAS-IUD, and there is no reason to believe that this would be differential by exposure group (e.g., breastfeeding vs. not breastfeeding at the time of IUD insertion). So the absolute incidence rates may not be entirely accurate because of potential underestimation due to underreporting or inaccurate coding; or potential overestimation if the algorithm identifies outcomes (e.g., uterine perforation) that are not true cases. However, the ratios should provide an unbiased estimate of any differential risk between exposure groups. We will also assess rates of uterine perforation and IUD expulsion in the literature to provide an external context for the incidence rates.

There is potential for misclassification and missingness of breastfeeding status at the time of IUD insertion. Data sources obtain information for this variable in different ways, with some utilizing linkage to well-child visits for the infant and others using data from the woman's chart either for postpartum visits or on the date of IUD insertion. The complexity of identifying the information within the charts is somewhat mitigated through the involvement of both clinicians and seasoned data informaticists working within each health care system who have experience with identifying such information. Further, the classification of breastfeeding as yes or no is a crude dichotomy and does not follow the potential biological mechanism for breastfeeding to affect uterine perforation or IUD expulsion. For example, breastfeeding once per day differs from eight times per day (the recommendation from one research partner), and thus combining all breastfeeding into one category combines a heterogeneous experience.

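### Protocol 9.9 says the ratios should be unbiased even if the algorithm counts false cases; an equal false-positive rate in both groups would pull any hazard ratio other than 1 toward 1

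*Protocol*

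**What the plan says.** Protocol Section 9.9 discusses two outcome errors together. Cases may be missed or recorded late, because a woman must seek care before an outcome is diagnosed; the section sees no reason for this to differ by exposure group. It then says absolute rates may be too low through underreporting or inaccurate coding, or too high through "potential overestimation if the algorithm identifies outcomes (e.g., uterine perforation) that are not true cases". The next sentence covers both: "However, the ratios should provide an unbiased estimate of any differential risk between exposure groups".

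The same section says the algorithms were validated in all four databases before ICD-10-CM coding came into use. It adds: "No formal validation of the algorithms with ICD-10-CM codes to identify uterine perforation or IUD expulsion will be done". Outcome rates before and after the coding change will be compared instead (SAP 6.3.3, planned Table 34.1). Neither document reports a PPV, sensitivity or specificity for perforation.

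Power in Protocol 9.5, Table 4 is at the two-sided 0.05 "level based on a perforation risk of 1.3 per 1,000 insertions and the percentage of insertions expected for the exposure groups of interest". There is no allowance for outcome misclassification. The only sensitivity analysis planned for the primary objectives is covariate adjustment in an unweighted Cox model (SAP 6.2.1).

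**The concern.** The two errors act differently on a ratio. Missing the same fraction of cases in each group scales both rates by the same factor, which cancels. Adding the same rate of false cases to each group adds a constant to numerator and denominator, which does not cancel. The non-differentiality argument in Section 9.9 is made only for missed or late outcomes, yet the conclusion is extended to false cases. Perforation is expected at about 1.3 per 1,000, so a specificity very slightly below 1 is enough to matter.

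This is a safety question, and the bias runs toward finding no increase. Section 9.9 gives avoidance of exactly that error as its reason for not adjusting for multiplicity. A reader who relies on the unbiasedness sentence could take a null or modest hazard ratio as more reassuring than the design allows.

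**Working it through.** **Inputs from the documents.** Primary objective 1: 60,000 insertions, 60:40 allocation, 1.3 per 1,000, two-sided alpha 0.05, stated power 85% at hazard ratio 2.0 (Protocol 9.5, Table 4). Expected events: 60,000 × 0.0013 = 78.

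**Assumed.** The PPV among unexposed cases, PPV0: 0.90, 0.80 and 0.70. False cases arise at the same rate in both groups.

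**1. Reproduce the stated figure.** Schoenfeld power = Φ(√(D·p·(1−p))·ln HR − 1.96). With D = 78 and p = 0.6, √18.72 = 4.327; 4.327 × 0.693 = 2.999; Φ(1.039) = 85.1%. The whole objective 1 row reproduces: 41.9, 67.8, 85.1, 93.9 and 97.8% against 42, 68, 85, 94 and 98.

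**2. Missed cases only.** With sensitivity s in both groups, HR_obs = (s·HR·r0)/(s·r0) = HR. Only events are lost: s = 0.8 leaves 62.4 events and 76% power, with the ratio still 2.0.

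**3. False cases only.** Let false cases occur at f times the true unexposed rate, f = (1 − PPV0)/PPV0. Then HR_obs = (HR + f)/(1 + f) = 1 + PPV0·(HR − 1). If HR = 1, HR_obs = 1.

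**4. Power for objective 1 at a true hazard ratio of 2.0.** Two event counts are possible. (A) The 78 events already include false cases. (B) The 78 are true cases and false ones are added: D = 78 × (1 + f/1.6), where 1.6 = 0.4 + 0.6 × 2.

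| PPV0 | f | HR_obs | Power, A (78 events) | Events, B | Power, B |
|---|---|---|---|---|---|
| 1.00 | 0 | 2.00 | 85% | 78 | 85% |
| 0.90 | 0.111 | 1.90 | 79% | 83 | 82% |
| 0.80 | 0.250 | 1.80 | 72% | 90 | 78% |
| 0.70 | 0.429 | 1.70 | 63% | 99 | 73% |

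**5. Objective 2, same formulas.** For each 5:70 comparison (168,750 × 0.0013 = 219.4 events, p = 5/75, stated 73%), PPV0 of 0.90, 0.80 and 0.70 gives 66, 58 and 50% under A, and 70, 67 and 64% under B. For the 20:70 comparison (263.3 events, p = 20/90, stated above 99%), power stays at 95% or more throughout.

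**6. In terms of specificity.** A specificity of 99.95% adds about 0.5 false cases per 1,000. The result depends on the true unexposed risk.
- At 0.9 per 1,000 (all non-breastfeeding women in the European cohort study, Protocol 9.5): (1.8 + 0.5)/(0.9 + 0.5) = 1.64.
- At 1.7 per 1,000 (non-breastfeeding, within 36 weeks of delivery, Protocol Table 2): (3.4 + 0.5)/(1.7 + 0.5) = 1.77. This is closer to objective 1, which is limited to women within 52 weeks postpartum.

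**7. Which correction works.** One PPV applied to both groups leaves (PPV·E1/Y1)/(PPV·E0/Y0) = (E1/Y1)/(E0/Y0), the uncorrected ratio. Under an equal false-positive rate with PPV0 = 0.80 and HR = 2, the exposed PPV is 2/(2 + 0.25) = 0.889. Only the group-specific values recover the truth: 1.80 × 0.889/0.80 = 2.0.

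**The case against.** The strongest reply is that this is one hedged sentence in a limitations section. No estimator, test or SAP rule depends on it, and the SAP does not repeat it. That is fair as to severity, but the sentence still tells readers how to interpret the ratios, and no other section corrects it.

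The plan also has controls on false cases. Outcomes draw on physician notes and validated algorithms (4.6.2), cases can be classed as undetermined (9.3.3), one site's text processing excludes negated terms and family history (9.6.4), another may build a review form for outcomes (9.6.3), and rates are compared across the coding change. These make a high PPV plausible, but confirmation of all cases is not specified and no figure is given. A before-and-after comparison of rates would not reveal offsetting changes in sensitivity and specificity.

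It may be said that equal PPV in both groups preserves the ratio. It does, but when there is a real effect this requires more false cases per insertion among the exposed, which the protocol neither states nor justifies.

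On power, the 1.3 per 1,000 is a 1-year figure from another study, while follow-up here has no maximum. More than 78 events are plausible, which could offset some power loss but would not remove the attenuation. Large effects are safe from being missed: at the hazard ratio of 3.3 suggested by the breastfeeding relative risk within 36 weeks (Protocol Table 2), PPV0 = 0.70 gives 1 + 0.7 × 2.3 = 2.61, with about 99% power at 78 events.

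**Conclusion.** The unbiasedness statement is correct for non-differential missed cases and incorrect for non-differential false positives. At a true hazard ratio of 2.0 and an assumed PPV0 of 0.90 to 0.70, the observed ratio would be 1.90 to 1.70. Objective 1 power would be about 79% to 63% if false cases are inside the 78 events, or about 82% to 73% if they are additional. These figures rest on the assumed PPVs, an equal false-positive rate in both groups, and the protocol's own event count.

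A reader might infer three stronger things that the documents do not support. First, that Table 4 is wrong: it reproduces on its own inputs and is optimistic only to the extent that false cases occur. Second, that the primary tests are invalid: at a hazard ratio of 1, an equal false-positive rate leaves the ratio at 1. Third, that the actual loss is known: no PPV or specificity is reported, and nothing shows that the validation study holds PPVs by site or by exposure. If false positives differ by exposure, the bias could go either way.

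**What to change.** In Protocol 9.9, limit the unbiasedness sentence to missed cases. State that non-differential false positives bias the ratio toward 1 and that differential ones could bias it in either direction.

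Add one quantitative bias table to the SAP for objectives 1 and 2. It should either subtract a common false-positive rate from both groups over a stated range, or use exposure-specific PPVs if the sponsor confirms that the validation study provides them. Uncertainty in those inputs should be carried into the intervals. A single PPV, pooled or per site, should not be applied to both exposure groups, because it cancels within the ratio.

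The cost is a text change, one extra table, and a less favourable limitations statement. If exposure-specific PPVs do not exist, the range-based version needs no new data.

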9.10 Other aspects

RTI-HS will serve as a coordinating center for this project and will coordinate the activities of the four research partners and Bayer (e.g., ensure that timelines are being met and facilitate communications). RTI-HS will receive deidentified person-level data from research partners and perform the pooled analyses. Person-level data will not be shared with Bayer. Data on IUD *brand* may be assessed at each site but will not be included in the datasets transferred to RTI-HS for data analysis. Overall data on IUD type, combined across all sites, will be shared with Bayer. Deidentified research partner data on IUD type (not IUD brand) may be shared between the respective research partner and RTI-HS, but will not be provided to Bayer.

RTI-HS will be the primary author for the protocol, statistical analysis plan, and a study report for this PMR study. The study report will be submitted to Bayer, and Bayer will submit the report to the FDA. RTI-HS will solicit and incorporate input from the research partners at each site and the Bayer study team for the protocol, statistical analysis plan, and study report.

10. Protection of human subjects

This is a noninterventional study using secondary data collection and poses only minimal risk for patients (e.g., potential for breach of confidentiality within health plan due to extraction of data from records). All data collected in the study will be deidentified, minimizing risk of breach of confidentiality with regard to personal identifiers or health information.

RTI-HS will obtain approval or exemption from the RTI International IRB before conducting the study. KPNC, KPSC, KPWA, and RI will also obtain approval or exemption from their IRBs before conducting the study. Data protection and privacy regulations will be observed in all aspects of data storage and analysis.

11. Management and reporting of adverse events/adverse reactions

This research study will use only data that have already been collected at the time the research was performed (i.e., secondary data analysis). The outcomes of uterine perforation and IUD expulsion will be reported in aggregate with the study results. Based on current guidelines from ISPE (ISPE, 2015) and the EMA (EMA, 2014), noninterventional studies such as the one described in this protocol, conducted using medical chart reviews or electronic claims and health care records, do not require reporting of adverse events or reactions.

12. Plans for disseminating and communicating study results

In Section V of *Guidelines for Good Pharmacoepidemiology Practices (GPP)*, the ISPE contends that “there is an ethical obligation to disseminate findings of potential scientific or public health importance” (ISPE, 2015); for example, results pertaining to the safety of a marketed medication; “...the marketing authorization holder should communicate to the Agency and the competent authorities of the Member States in which the product is authorized the final manuscript of the article within 2 weeks after first acceptance for publication.”

Results of this study will be published following guidelines, including those for authorship, established by the International Committee of Medical Journal Editors (ICMJE, 2016). When reporting results of this study, the appropriate Strengthening the Reporting of Observational Studies in Epidemiology checklist will be followed (von Elm et al., 2008). The Consolidated Standards of Reporting Trials (CONSORT) statement (Moher et al., 2001) refers to randomized studies, but provides useful guidance applicable to nonrandomized studies.

The publication committee, which includes representatives from Bayer, investigators of each partner institution, and RTI-HS, will agree upon a publication plan that will result in collaborative and inclusive publication(s) and presentation(s) based on these study results—following publication guidelines of the International Committee of Medical Journal Editors (ICMJE, 2016). Bayer will ensure that the FDA is informed prior to any publication. Communication via appropriate scientific venues, e.g., International Society for Pharmacoepidemiology, will be considered.

13. List of references

- Austin PC. An introduction to propensity score methods for reducing the effects of confounding in observational studies. *Multivariate Behav Res.* 2011 May;46(3):399-424.
- Austin PC. The performance of different propensity score methods for estimating marginal hazard ratios. *Stat Med.* 2013 Jul 20;32(16):2837-49.
- Austin PC. The use of propensity score methods with survival or time-to-event outcomes: reporting measures of effect similar to those used in randomized experiments. *Stat Med.* 2014 Mar 30;33(7):1242-58.

Annex 1. List of stand-alone documents

None.

Document Type:	Statistical analysis plan
Official Title:	Study on the A ssociation of Uterine P erforation and IUD E xpulsion With Breastfeeding Status at the Time o f IUD Insertion and Postpartum Timing of IUD Insertion in Electronic Medical Record Databases - A Postmarketing Requirement for Mirena (APEX IUD)
NCT Number:	NCT03754556
Document Date:	24 Oct 2018

Statistical analysis plan

Study on the A ssociation of U terine P erforation and I UD E xpulsion With Breastfeeding Status at the Time of I UD Insertion and Postpartum Timing of IUD Insertion in Electronic Medical Record Databases – A Postmarketing Requirement for Mirena (APEX IUD)			
Medicinal product:	Mirena®, Skyla®, Liletta®, Kyleena®, and ParaGard® intrauterine devices		
Study Purpose:	
This is a United States postmarketing requirement study assessing outcomes of uterine perforation and intrauterine device (IUD) expulsion in association with breastfeeding, time since delivery, and type of IUD.
 
The study aims to quantify the risk of uterine perforation and IUD expulsion for the following comparisons:
 
 • Women who are breastfeeding at the time of IUD insertion versus not breastfeeding at the time of IUD insertion • Women who had a first observed IUD insertion within different time periods postpartum (i.e., ≤ 6 weeks, > 6 weeks and ≤ 14 weeks, > 14 weeks and ≤ 52 weeks) versus women who had their first observed IUD insertion more than 52 weeks postpartum, including women without a recorded delivery within the past 52 weeks 
This study will also assess the risk of perforation and expulsion (separately) by type of IUD. In addition, this study aims to assess the following interactions:
 
 • The extent to which type of IUD (levonorgestrel-releasing vs. copper IUD) modifies the association between perforation and/or expulsion and breastfeeding status and/or postpartum status • The extent to which breastfeeding status modifies the association between perforation and/or expulsion and postpartum status 		
IMPACT No.:	19682	Protocol Date:	29 June 2018
SAP Version, Date:	Version 2.0, 24Oct2018	SAP includes TLF Specification:	yes  no 
Author:	PPD  RTI Health Solutions [name]		

Confidential

